**Reviewer 3 (optional)**

Date

1    **Scientific Assessment: Method 3**

2    **Study Title:** *Effects of anodal transcranial direct current stimulation (a-tDCS) on naming in*  
3    *patients with non-fluent aphasia.*

4    **PI:** *[name] CCC-SLP*

5    **Co-investigator:** *[name] CCC-SLP*

6       • **Is the rationale for the study clearly stated and is the rationale scientifically**  
7    **sound?**

8    The emerging evidence of the relationship between working memory (WM) and naming  
9    offers a unique opportunity to investigate the effects of upregulation of WM systems and the  
10   effect on naming in nonfluent aphasia. Transcranial direct current stimulation (tDCS) is a  
11   non-invasive neuromodulation tool that presents a low current that induces bi-directional  
12   polarity-dependent changes in the cortex to facilitate focal, prolonged shifts in cortical  
13   excitability at or around the time stimulation is provided . Anodal tDCS (a-tDCS), in which  
14   the positively charged electrode is placed over the targeted cortical region, has been shown  
15   to increase cortical excitability (upregulation), similar to long-term potentiation (LTP).  
16   Combining a-tDCS with behavioral-based approaches has been suggested to enhance the  
17   learning process and increase the likelihood of retention. Although there is no specific  
18   neurophysiologic evidence to identify suppression of dorsolateral prefrontal cortex (DLPFC)  
19   in participants with aphasia, it has been implicated in naming deficits due to its role in  
20   working memory. tDCS has been applied to the DLPFC to target working memory, to  
21   date, there have been no investigations using a-tDCS to the DLPFC to influence naming  
22   skills in non-fluent aphasia. The overarching goal of this study is to explore the relationship  
23   between WM and naming by investigating the effects of a-tDCS to left DLPFC on naming  
24   accuracy and naming reaction times (RTs) in non-fluent aphasia. The primary purpose of this  
25   study is to 1) establish feasibility and safety of applying a-tDCS to the left DLPFC in patients  
26   with Broca's aphasia combined with behavioral naming treatment.  
27

28       • **Are the aims and corresponding hypothesis clearly stated?**

29    **Aim 1:** *Determine feasibility and safety of applying a-tDCS to the left DLPFC in Broca's aphasia.*  
30   Two conditions: 1)a-tDCS (2mA for 20 minutes) will be applied over the left DLPFC followed  
31   immediately by behavioral naming therapy and 2) sham tDCS followed immediately by  
32   behavioral naming therapy will be presented to participants with non-fluent aphasia. *Hypothesis*  
33   1: no adverse events will be reported during or following this treatment and all participants will  
34   complete the study.  
35

36   **Aim 2:** *Identify effectiveness of a-tDCS to the left DLPFC combined with behavioral naming*  
37   *treatment in Broca's aphasia and establish a sample size for future investigations of this nature.*  
38   A small sample size will be used in this study to investigate effectiveness of the use of a-tDCS  
39   to the left DLPFC with behavioral therapy to target naming in non-fluent aphasia. *Hypothesis 2:*  
40   Improvements in working memory, naming reaction time and naming accuracy will be observed  
41   after the real a-tDCS condition but not after the sham a-tDCS condition.  
42

1     • **Is the primary outcome (and secondary outcomes, as appropriate) clearly  
2     defined?**

3     Primary outcomes include: naming accuracy on treated and control items, naming RTs on  
4     treated and control items, performance on WM tasks, and motor speech tasks.

5     • **Are there adequate preliminary data in the literature (or from the investigator) to  
6     justify the proposed research? Has an adequate literature review been done to  
7     support this study?**

8  
9     WM systems are short-term, temporary stores that are activated when active manipulation of  
10    items is necessary. It could be argued that all linguistic tasks invoke WM systems since the  
11    execution of any linguistic task requires the ability to maintain activation of a representation until  
12    the targeted linguistic process is complete. Indeed, the close relationship between language  
13    and WM is represented in many WM models. Over the past few decades, there has been  
14    increasing recognition that aphasia is frequently accompanied by deficits in WM systems.  
15    Furthermore, such deficits adversely impact linguistic performance in aphasia. Accordingly,  
16    treatment protocols are being developed on the premise that treatments aimed at improving WM  
17    systems will improve linguistic function in aphasia. While a variety of WM treatment  
18    protocols have been designed to improve linguistic processes such as oral reading, repetition,  
19    or comprehension abilities in aphasia, there are no such studies in the area of naming. Yet, one  
20    particular WM component, subvocal rehearsal processes, may play a crucial role in naming  
21    abilities in aphasia. Subvocal rehearsal processes are activated when verbal memory traces  
22    must be refreshed. Such processes become vital in cue-based protocols where the  
23    individual is asked to self-generate cues needed to increase lexical access to the object name.  
24    Within this context, it may be that subvocal rehearsal systems might be crucial during picture  
25    naming processes as it functions to preserve and refresh information, facilitating convergence of  
26    activation onto targeted representations. This becomes a useful compensatory strategy when  
27    there are lexical access and retrieval failures. However, the ability to engage in subvocal  
28    rehearsal processes are likely deficient in individuals with aphasia, which impacts not only  
29    immediate treatment effects, but also long-term treatment effects since cue self-generation as a  
30    compensatory strategy would be limited.

31    The application of a-tDCS to the language regions in combination with behavioral-based  
32    approaches has resulted in improved language outcomes in individuals with aphasia. In  
33    addition, a-tDCS applied to the left DLPFC has resulted in improved performance on WM tasks  
34    in healthy individuals, individuals with Parkinson's Disease and stroke. a-tDCS is ideally  
35    suited to upregulate the left DLPFC and may potentially activate subvocal rehearsal processes  
36    needed in order to improve self-generation of cues during naming. However, there have been  
37    no investigations to date using neuromodulation techniques to the DLPFC to target naming  
38    skills in aphasia.

39  
40     • **Is the question or hypothesis being tested providing important knowledge to the  
41     field?**

42  
43    The findings from the proposed study will lay the foundation for a larger clinical trial which will  
44    in turn have a significant impact on individuals with aphasia given that naming deficits are a  
45    common symptom in this population. As the presence of naming deficits has a negative  
46    relationship to emotional well-being and functional communication, treatment that  
47    improves naming deficits will positively influence quality of life in many of these individuals.  
48    The approach taken to remediate naming deficits in aphasia is to treat impaired WM systems

1 on the premise that certain cognitive processes underlie linguistic functions in aphasia. This  
2 approach represents a departure from most behavioral-based naming treatment approaches,  
3 but reflects a growing recognition that WM systems in individuals with aphasia impact  
4 linguistic performance . The addition of a-tDCS as a neuromodulation tool to increase  
5 cortical excitability (upregulate) the working memory center to target naming is a novel  
6 approach in aphasia. These findings, , will provide valuable information regarding the role  
7 WM plays in naming and the potential benefit of using neuromodulation to the DLPFC to  
8 influence naming in aphasia.

9

- 10 • **Is the design of the study appropriate for the questions that are posed?**

11

12 *Treatment Design:*

13 A single subject cross-over design with a 4 week wash out period will be used. Two treatment  
14 conditions will be presented. The sham (SHAM) condition will consist of presentation of sham  
15 tDCS for 20 minutes followed by behavioral naming treatment. The real treatment condition  
16 (REAL) will consist of 20 minutes of a-tDCS to the left DLPFC followed by behavioral naming  
17 treatment. The length of behavioral naming treatment will depend on how long each participant  
18 takes to go through the treatment stimuli twice. A SHAM-REAL sequence will be used across all  
19 participants. Although order effects may be introduced using the same sequence across  
20 participants, the small number of participants makes it difficult to interpret any data that comes  
21 from using a counterbalanced presentation of treatment.

22 Treatment will be provided over five consecutive days. A minimum of a one-month washout  
23 period will be provided between the two conditions (Figure 1). Prior to initiating the REAL  
24 treatment condition, the naming RTs obtained on the second word list during the pre-treatment  
25 testing period (prior to the initiation of the SHAM condition) will be compared to the naming RTs  
26 obtained after the washout period. RTs will be analyzed to ensure that no lasting treatment  
27 effects remain after the SHAM condition. If performance on naming RTs is +/- 1 standard  
28 deviation from the individual's benchmark mean, the REAL treatment condition will begin. If  
29 performance on naming RTs is > +/- 1 standard deviation from the individual's benchmark  
30 mean, REAL treatment will be postponed until the mean RTs fall within +/- 1 standard deviation  
31 of the benchmark. Periodic checks will be conducted weekly to identify when to begin REAL  
32 condition. Once there are minimal differences between naming RTs on the second word list,  
33 the REAL treatment will be initiated.

34

[figure not shown]
35 *Outcome measures:*

36 Two different word lists will be generated; a different list will be used for each treatment  
37 condition to control for exposure and learning effect. Pretreatment testing outcome measures will  
38 be recorded for 5 consecutive days for each outcome measure including: 1) naming accuracy 2)  
39 naming RTs on both word lists 3) performance on motor speech tasks and 4) performance on  
40 working memory tasks. Stability of baseline performance, defined as no more than 20%  
41 difference between scores, will be obtained in five consecutive sessions. In addition, outcome  
42 measures will be obtained immediately after each treatment session. Five maintenance  
43 outcome measures will also be obtained upon completion of treatment. These sessions will take  
44 place at the Clinical Translational Science Institute (CTSI) on [name] on the University  
45 of MN campus. An adverse events questionnaire will also be given after each treatment session  
46 as a mechanism of participants reporting any discomfort.

47  
48  
49

50

1 **Figure 1. Treatment Schedule**

6 *tDCS Protocol.*

7 Treatment sessions will take place at the University of MN Clinical Translational Science  
8 Institute. Each participant will be seated comfortably in a chair. A swim cap will be placed on  
9 the participant's head to identify cranial landmarks for accurate electrode placement. The area  
10 referred to as F3 by the International 10/20 system for electroencephalogram electrode  
11 placement has been established as the optimal location for targeting the left DLPFC.  
12 The F3 region will be located by marking the vertex (the midpoint between left and right tragus  
13 and midpoint between nasion and inion), measuring the head circumference. When these  
14 measurements are entered into the Beam F3 Locator Software, additional values are provided  
15 to reliably identify the location of F3. Once F3 has been established, two saline soaked surface  
16 sponge electrodes (35cm) will be prepared and placed. For optimal anodal stimulation to the  
17 DLPFC, the anode will be placed over F3 and the cathode will be placed over the right  
18 supraorbital region. A current of 2mA will be delivered for 20 minutes  by a multichannel  
19 transcranial current stimulator (Starstim, Neuroelectrics Corporation; Cambridge, MA). a-tDCS  
20 will be applied before and during behavioral treatment in the design specified below.

25 *Behavioral-Based Naming Treatment Protocol.*

27 *Stimuli.* Eighty black-and-white line drawings will be obtained from on-line clip art websites.  
28 Picture names will be normed using five to ten English-speaking volunteers who will be asked to  
29 provide the names of the pictures. Cues words will be paired with the pictures if the words  
30 represent an associative or thematic relationship. Therefore, the words will be chosen that  
31 represent a concrete attribute (e.g., the picture, SHARK, is paired with the cue word *teeth*),  
32 location (e.g., the picture, SHARK, is paired with the cue word *ocean*), and either function or  
33 category (e.g., the picture, SHARK, is paired with the cue word, *fish*). The selection criteria for  
34 choosing these particular attributes is based on a classification criteria of thematic relations .  
35 Moreover, there is empirical evidence that that associative relations would prove beneficial in a  
36 naming treatment paradigm . Commonly used phrases (e.g., *great white shark*) or compound  
37 words (e.g., *bluefin shark*), synonyms or antonyms will be excluded. These cue words will be  
38 obtained from a semantic features normative database , which provides not only semantic

1 features information but categorical information as well. Two lists of 20-items will be created,  
2 which will be presented to each participant in order to avoid presenting the same list across the  
3 conditions. Pictures used in both lists will be balanced in terms of visual complexity and  
4 familiarity ratings. Words used in all conditions will be balanced in terms of lexical frequency  
5 and word length. Familiarity ratings will be obtained from a normative database. Visual  
6 complexity ratings will be also obtained from a group of 20 individuals using the instructions and  
7 rating scales as reported in Snodgrass and Vanderwart's article. The CELEX database, will  
8 be consulted to determine lexical frequency of the words (cues) used in the study. An additional  
9 40 pictures will be selected for a control (untreated) list that will be used only during baseline  
10 and post-treatment testing. Performance on treated and untreated lists will be compared to  
11 determine treatment effects and possible generalization effects.

12  
13 *Naming Treatment Procedures.* All participants will be provided the same protocol, which will  
14 highlight the process of rehearsing the cues associated with the picture name. Treatment  
15 sessions will last until each participant has gone through the treated items twice. To insure  
16 control during the protocol, a graduate student trained in the protocol will administer the  
17 treatment steps. She will be blinded to the objectives of the study and conditions that are being  
18 administered. Treatment sessions will be video recorded for reliability purposes. To insure that  
19 she is not aware of when tDCS is being administered, a screen will be in place between the  
20 tDCS machine and the treatment table. The protocol is provided in Table 1.

21  
22 **Table 1. Naming Treatment Protocol.**

Steps Involved in Naming Treatment Protocol	
Picture Presentation	Participant will be asked to name the picture. If she/he is unable to provide the name within 10 seconds, the name will be provided.
Cue Presentation	Cues that accompany the picture will be presented. He/she will be asked to read each cue word as it is presented. If he/she is unable to read the word spontaneously within 10 seconds, he/she will be asked to repeat each word after the clinician.
Cue Rehearsal	Both picture and cues are taken away. Participant is asked to rehearse the cue words silently for 10 seconds.
Cue Self-Generation	Participant will be asked to generate all three cues. For each instance that the participant is unable to provide a cue within 10 seconds, the cues will be provided. Once the cues have been provided, the participant will then be asked to provide the picture name.
Picture + Cue Presentation	If the participant is unable to provide the name, the cues will be read, or if he/she is unable to read spontaneously, he/she will be asked to repeat after the clinician. If she/he is still unable to provide the picture name after the cue review, it will be provided.
Picture + Cue Review	Once the cues and picture are laid out on the table, the clinician will read each cue and name the picture. The participant will be encouraged to read/repeat with the clinician.

1  
2     • **Have the validity and reliability of measures been established or are there**  
3     **methods proposed for establishing validity and reliability?**

4  
5     Approximately 20% of each of the participant's behavioral treatment sessions will be  
6     observed by the co-investigator in order to obtain procedural integrity. Steps of the treatment  
7     protocol will be scored using a binary (+/-) coding system. Point-by-point agreement will be  
8     obtained. Reliability in scoring naming error types will also be obtained using a table that  
9     lists the most common aphasic naming errors, definitions and examples of each error type.  
10    Point-by-point agreement will be obtained.

11  
12     • **Is the proposed subject population appropriate?**

13     Participants will be recruited via emails sent to Twin Cities metro area hospital and  
14     aphasia/stroke support groups. Potential participants will then be screened for eligibility for  
15     the study.

16     **Screening.** Potential participants will be seen for 2-3 sessions to undergo comprehensive  
17     cognitive-linguistic assessment to determine eligibility for the study. This assessment will  
18     take place within the participant's home to provide a comfortable, natural environment for the  
19     potential participant. Behavioral assessment measures will include the Western Aphasia  
20     Battery (WAB) which will be used to obtain overall language function via the WAB Aphasia  
21     Quotient (WAB AQ), the Boston Naming Test (BNT) in order to obtain naming function,,  
22     Apraxia Battery for Adults (ABA-2) in order to determine apraxia of speech severity, and  
23     working memory tasks to determine subvocal rehearsal processes and phonological short-  
24     term store abilities.

25     These participants must meet the following inclusionary criteria:

26         • a diagnosis of moderate-moderately severe non-fluent aphasia based on  
27         performance on the WAB (see above screening procedures).  
28         • a diagnosis of moderate-moderately severe non-fluent aphasia based on  
29         performance on the BNT (see above screening procedures).  
30         • a diagnosis of mild-moderate apraxia of speech (AoS) based on performance on the  
31         ABA-2 (see above screening procedures).  
32         • completion of high school or GED  
33         • normal or corrected-to-normal vision  
34         • adequate hearing acuity for 1:1 conversational exchanges  
35         • use of English as primary language  
36         • a vascular lesion in the dominant left hemisphere, not in the region of the DLPFC  
37         verified by an MRI scan within six months of the start of the study.

38     These participants must also meet the following exclusionary criteria:

39  
40         • no previous history of neurological- or psychiatric-based illnesses or disease,  
41         language or learning disabilities, or alcohol/substance abuse  
42         • no history of seizures  
43         • no metal implants in the head (except dental fillings)  
44         • no lesion in the left DLPFC confirmed by MRI

1       • no current pregnancy

2  
3 Individuals who meet the inclusionary/exclusionary criteria and who are still interested in  
4 participating will then be consented to participate in the research study. After four  
5 participants have been identified as eligible and consented for the study, recruitment will  
6 stop.

7       • **Are statistical considerations, including sample size and justification, estimated  
8 accrual and duration, and statistical analysis clearly described and adequate to  
9 meet the study objectives?**

10  
11 Descriptive statistics such as naming percent accuracy, range of naming percent accuracy,  
12 number of cues generated independently, and rates of naming errors, will be collected. Although  
13 normally distributed data is not expected in this small sample size and in this population of  
14 participants, a Shapiro-Wilk test of normal distribution will be conducted to report the  
15 distribution. Single subject analysis techniques will be used such as visual inspection, graphical  
16 analysis and confidence interval comparison.

17  
18 *Aim 1.* To address the feasibility and safety aim, the number and type of adverse events for  
19 each patient will be recorded and presented. In addition, the number of participants who failed  
20 to complete the study will be recorded and factors recorded. To the extent possible, the  
21 participants will be asked to continue to participate in the assessments to allow a consideration  
22 of intent to treat analysis.

23  
24 *Aim 2.* Means and 95% confidence intervals will be plotted and used for comparison of naming  
25 RTs, working memory performance and motor speech performance across treatment conditions  
26 for each subject (Deng, et al. 2013). Naming accuracy performance will be analyzed using  $d'$   
27 statistics for lexical data to determine magnitude of treatment effect. The effect size will be  
28 interpreted using benchmarks proposed by Beeson and Robey (2006) for lexical retrieval  
29 treatments: small ES = 4.0, medium ES = 7.0, large ES = 10.1. Naming RT mean and  
30 confidence intervals will be analyzed for changes within and across treatment conditions using  
31 visual inspection.

32  
33       • **Are all the proposed tests or measurements requested necessary to answer the  
34 scientific question?**

35 Yes. The proposed measures will allow investigators to report the feasibility and safety of  
36 the use of a-tDCS. The measures will also allow investigators to identify individual treatment  
37 effects of a-tDCS to left DLPFC combined with behavioral naming therapy on naming in non-  
38 fluent aphasia and through visual inspection and graphical analysis, compare effects to sham  
39 treatment. Naming RT and accuracy are sensitive measures of the participant's retrieval and  
40 learning of treated items. Motor speech performance will allow us to track changes in motor  
41 planning and sequencing abilities, which can influence naming RT and naming accuracy.  
42 And, performance on working memory tasks will allow for investigation of the influence of  
43 WM on naming and to provide additional evidence that a-tDCS to the left DLPFC may  
44 influence WM in individual participants.

45  
46       • **Are the investigators well qualified to conduct this study?**

47  
48 **Key Personnel**

1                   **Name**

2                   [name] CCC-SLP

3                   **Affiliation**

4                   University Wisconsin River Falls

5                   **Role**

6                   PI

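### Four participants cannot establish safety: zero adverse events would leave a per-patient risk of up to 52.7% (one-sided 95%) or 60.2% (two-sided), and Aim 1 specifies no summary by SHAM and REAL

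*Combined protocol and SAP*

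**What the plan says.** All references are to the combined protocol and SAP.

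- **Rationale section.** The primary purpose of the "study is to 1) establish feasibility and safety of applying a-tDCS to the left DLPFC in patients" with Broca's aphasia, combined with behavioral naming treatment.
- **Aims section, Aim 1.** The SHAM and REAL conditions are described, followed by Hypothesis "1: no adverse events will be reported during or following this treatment and all participants will" complete the study. The text does not say which condition the treatment in that sentence refers to. It gives no grade, seriousness or relatedness.
- **Outcome measures.** An adverse events questionnaire follows each treatment session "as a mechanism of participants reporting any discomfort". The visible text gives neither its content nor a rule for which answers count as adverse events.
- **Subject population section.** "participating will then be consented to participate in the research study. After four" "participants have been identified as eligible and consented for the study, recruitment will" stop. No replacement for dropout is mentioned.
- **Statistical considerations, Aim 1.** "To address the feasibility and safety aim, the number and type of adverse events for" "each patient will be recorded and presented". Non-completers are counted and the factors recorded. No split by condition, interval or threshold is given.
- **Statistical considerations, Aim 2.** Reaction time, working memory and motor speech are compared across treatment conditions, with 95% confidence intervals.
- **Treatment Design.** Every participant receives SHAM first, then REAL after a washout of at least a month. The plan acknowledges that order effects may arise.

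**The concern.** The claim attached to the safety data is stronger than four people can support, and the zero-event hypothesis tells the reader little whichever way it comes out. If no events are reported, the natural conclusion under the stated purpose is that safety has been established, yet a large true risk remains compatible with the data. If one mild complaint is reported, the hypothesis is contradicted for a reason that may have no bearing on safety.

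Aim 1 also does not ask for the one display that would help a reader most: which events occurred under SHAM and which under REAL, and how many people actually received each. Because SHAM always comes first, a participant who leaves before REAL has had no active stimulation but would still appear in a per-patient table of four. The study is meant to lay the ground for a larger trial, so an overstated safety conclusion would carry forward.

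**Working it through.** **Inputs.** n = 4 (subject population section). Treatment runs over five consecutive days (Treatment Design), read here as five sessions per condition, hence 4 × 5 = 20 REAL sessions and 4 × 10 = 40 in all. The 95% level is borrowed from Aim 2, since Aim 1 states none. The documents give no event rate, so the rates below are assumptions shown over a range. There is no sample-size calculation behind n = 4 to reproduce.

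**1. What zero events would show.** The exact upper bound for 0 of n is 1 − a^(1/n).

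- One-sided 95%: 1 − 0.05^(1/4) = 52.7%.
- Two-sided 95%: 1 − 0.025^(1/4) = 60.2%.
- If one participant left before REAL, three would be exposed: 1 − 0.05^(1/3) = 63.2% (one-sided).

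The chance that no participant is affected is (1 − p)^4. At a true per-patient risk of 10%, 20% or 30% it is 65.6%, 41.0% or 24.0%.

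**2. What full completion would show.** For 4 of 4, the exact lower bound is 0.05^(1/4) = 47.3% (one-sided) or 0.025^(1/4) = 39.8% (two-sided).

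**3. How easily the hypothesis is contradicted.** Suppose any reported discomfort counts, with per-session rate q. With independent sessions, the chance of at least one event in s sessions is 1 − (1 − q)^s. At the other extreme, if each person either complains at every session or never, the exponent becomes the number of people, 4.

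| Assumed q | 40 sessions, independent | 20 REAL sessions, independent | Complete clustering within person |
|---|---|---|---|
| 1% | 33.1% | 18.2% | 3.9% |
| 2% | 55.4% | 33.2% | 7.8% |
| 5% | 87.1% | 64.2% | 18.5% |
| 10% | 98.5% | 87.8% | 34.4% |

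The independent columns are therefore the upper end, and the last column is the lower end under positive clustering.

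**4. What a REAL-SHAM comparison could show.** The most extreme paired result is all four participants having events under REAL only. The exact paired (McNemar) p-value is then 0.5^4 = 0.0625 one-sided, or 2 × 0.5^4 = 0.125 two-sided. Conventional two-sided significance is out of reach, and with a fixed order any difference would also be a difference between periods.

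**The case against.** The strongest reply is that this is a small descriptive pilot. The plan acknowledges its small sample, presents itself as groundwork for a larger trial, and elsewhere speaks of reporting feasibility and safety. This weakens the criticism of the word establish but does not remove it, because that word states the primary purpose and is paired with a zero-event hypothesis.

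Three stronger readings are tempting, and the documents do not support them.

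- **That the plan pools SHAM and REAL events.** It never says so. Aim 1 presents events per patient and is silent on condition. Because the questionnaire follows every treatment session, condition can be recovered. The gap is in the planned summary and not in data collection.
- **That a decision rule fails on a single complaint.** No test, threshold or go/no-go decision depends on Hypothesis 1. A complaint would be listed with its type. It would contradict the stated expectation and nothing more, and only if discomfort on the questionnaire counts as an adverse event. Whether a complaint under SHAM would count is also left open.
- **That a by-condition table would separate the effect of stimulation from sham.** It would not. The fixed order confounds condition with period, and four pairs cannot give a two-sided exact p-value below 0.125.

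It is also fair to say that the percentages in step 3 are illustrative and that independence overstates them if complaints cluster within person. The bounds in steps 1 and 2 need no assumed event rate or independence between sessions.

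**Conclusion.** The point holds as a mismatch between claim and evidence, plus an omission in the Aim 1 summary. With four participants, zero events remains compatible with a per-patient risk of up to 52.7% (one-sided) or 60.2% (two-sided), so it cannot establish safety. Completion by all four is compatible with a true completion rate as low as 47.3% or 39.8%. These figures rest on n = 4, independent participants and a 95% level.

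The chance that a minor complaint contradicts the hypothesis depends on the assumed rate, the degree of clustering, whether SHAM sessions count, and whether discomfort is an adverse event; the documents settle none of these. The absence of a specified SHAM/REAL split is real, contrasts with Aim 2, and can be remedied from data the trial already plans to collect. The change is worth making because it concerns the primary purpose and requires no change to the design, sample size or treatment.

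**What to change.** 1. In the Aim 1 analysis, tabulate adverse events and non-completion by participant and by condition (SHAM/REAL), with the number actually exposed to each condition and serious events shown separately. State whether discomfort reported on the questionnaire counts as an adverse event.
2. Give exact 95% intervals for the participant-level proportion with an event under REAL and for completion.
3. Replace the aim of establishing safety, and the zero-event hypothesis, with a descriptive statement that the study will provide preliminary safety data.
4. State that the REAL-SHAM contrast is descriptive only, because the fixed order confounds condition with period and the smallest attainable two-sided exact p-value with four pairs is 0.125.

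**Cost.** Revised wording and one table. The stated safety claim becomes less favourable. Condition is already known from the session, but recording severity or relatedness may need added fields on the form.
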